8.2.8 Black Box Warning

WARNING: EMBRYO-FETAL TOXICITY, HEMATOLOGIC TOXICITY, and VENOUS THROMBOEMBOLISM See full prescribing information for complete boxed warning.

EMBRYO-FETAL TOXICITY

Lenalidomide, a thalidomide analogue, caused limb abnormalities in a developmental monkey study similar to birth defects caused by thalidomide in humans. If lenalidomide is used during pregnancy, it may cause birth defects or embryo-fetal death. Pregnancy must be excluded before start of treatment. Prevent pregnancy during treatment by the use of two reliable methods of contraception. REVLIMID is available

only through a restricted distribution program called the REVLIMID REMS¹⁰⁰ program (formerly known as

the "RevAssist program")

HEMATOLOGIC TOXICITY.

REVLIMID can cause significant neutropenia and thrombocytopenia. For patients with del 5q myelodysplastic syndromes, monitor complete blood counts weekly for the first 8 weeks and monthly thereafter.

VENOUS THROMBOEMBOLISM

Significantly increased risk of deep vein thrombosis (DVT) and pulmonary embolism (PE) in patients with multiple myeloma receiving REVLIMID with dexamethasone.

8.2.9 Nursing/Patient Implications and Monitoring requirements

Effective contraception must be used by patients for at least 4 weeks before beginning lenalidomide therapy, during lenalidomide therapy, during dose interruptions, and for 4 weeks following discontinuation of lenalidomide therapy. Reliable contraception is indicated even where there has been a history of infertility, unless due to hysterectomy or because the patient has been postmenopausal naturally for at least 24 consecutive months. Two reliable forms of contraception must be used simultaneously, by females, unless continuous abstinence from heterosexual sexual contact is the chosen method. Females of childbearing potential should be referred to a qualified provider of

1.

contraceptive methods, if needed. Males receiving lenalidomide must always use a latex condom during any sexual contact with females of childbearing potential even if they have undergone a vasectomy.

- 2. Caution patient not to drive or use hazardous machinery until the potential sedative effects of the drug are known in the patient.
- 3. Caution patient to report leg swelling or shortness of breath, because of the risk of thrombosis/embolism
- 4. Counsel patient to report abnormal sensations in hands or feet, such as decreased sensation or dysesthesia. Paresthesias are often noted early before neuropathy develops.
- 5. Advise patient to immediately report rashes or fever.

Because of the embryo-fetal risk, lenalidomide is available only through a restricted program under a Risk Evaluation and Mitigation Strategy (REMS), the REVLIMID REMS[™] program (formerly known as the "RevAssist®" program). Required components of the REVLIMID REMS[™] program include the following:

- Prescribers must be certified with the REVLIMID REMS[™] program by enrolling and complying with the REMS requirements.
- Patients must sign a Patient-Prescriber agreement form and comply with the REMS requirements. In particular, female patients of reproductive potential who are not pregnant must comply with the pregnancy testing and contraception requirements.
- Pharmacies must be certified with the REVLIMID REMS[™] program, must only dispense to patients who are authorized to receive REVLIMID and comply with REMS requirements.

Further information about the REVLIMID REMS[™] program is available at http://www.revlimidrems.com or by telephone at [name].

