Females of childbearing potential (FCBP) must either commit to continued abstinence from heterosexual intercourse or begin TWO acceptable methods of birth control: one highly effective method and one additional effective method AT THE SAME TIME, at least 28 days before starting lenalidomide, during lenalidomide therapy, during dose interruptions, and for at least 28 days following discontinuation of lenalidomide therapy (refer to the patient resources materials or http://www.revlimidrems.com for more information).

Males receiving lenalidomide must agree to use a latex condom during any sexual contact with FCBPs even if they have undergone a successful vasectomy.

NOTE: A FCBP is any woman (regardless of sexual orientation, having undergone a tubal ligation, or remaining celibate by choice) who meets the following criteria:

- Has not undergone a hysterectomy or bilateral oophorectomy
- Has not been naturally postmenopausal for at least 12 consecutive months (i.e., has had menses at any time in the preceding 12 consecutive months).

FCBP should be referred to a qualified provider of contraceptive methods, if needed.

- 3.1.7 FCPB must have a negative urine or serum pregnancy test within 7 days prior to registration, and be willing to adhere to the scheduled pregnancy testing as required in the Revlimid REMS® program. NOTE: Should a woman become pregnant or suspect she is pregnant while participating in this study, she should inform her treating physician immediately.
- 3.1.8 Patients must be free of any prior malignancies for ≥1 year at the investigator's discretion.

NOTE: The exception to this would be currently treated squamous cell and basal cell carcinoma of the skin, carcinoma in situ of the cervix, breast, or bladder, or surgically removed melanoma in situ of the skin (stage 0) with histologically confirmed free margins of excision.

3.1.9 All study participants must be registered into the mandatory Revlimid REMS® program, and be willing and able to comply with the requirements of REMS®.

3.1.10 Patients must have the ability to understand and the willingness to sign a written informed consent prior to registration.

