4.4 Duration of Therapy & Early Withdrawal

Treatment may continue for up to one (1) year or until any of the following occur, resulting in early withdrawal from study treatment (or in some cases withdrawal from the study as a whole):

- disease progression
- inter-current illness that prevents further administration of treatment
- unacceptable toxicity
- patient decides to withdraw from study treatment (or study as a whole)
- general or specific changes in the patient's condition render the patient unacceptable for further treatment in the judgment of the treating investigator

Note: Patients who have not achieved PR or CR after 4 cycles should continue to be treated on the current protocol only if they have SD (i.e., not PD), AND if they do not have other options available that would present a more favorable risk/benefit ratio.

Patients will be removed (withdrawn) from study therapy for any of the criteria listed above. The PI and the Quality Assurance Monitor (QAM) at NU is to be notified of such events; the reason(s) for removal and the date the patient was removed are to be documented in the appropriate electronic case report form (eCRF). The patient should be followed as described below in Section 4.5.

Patients who withdraw consent from the study as a whole will be noted to have withdrawn from both treatment and any further follow-up.

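### Sections 3.1.6 and 8.2.9 give different natural-menopause limits, 12 and 24 consecutive months, for the lenalidomide contraception requirement

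*Combined protocol and SAP*

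**What the plan says.** Three places bear on this point.

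- **Section 3.1.6 (Inclusion Criteria)** first asks every patient to agree to effective contraception while on study. It then adds a stricter rule: "Females of childbearing potential (FCBP) must either commit to continued abstinence from heterosexual intercourse or begin TWO acceptable methods of birth control". A note defines an FCBP as a woman who has neither "undergone a hysterectomy or bilateral oophorectomy" nor "been naturally postmenopausal for at least 12 consecutive months". A parenthesis restates the menopause criterion: she "has had menses at any time in the preceding 12 consecutive months".
- **Section 8.2.9 (Nursing/Patient Implications and Monitoring requirements)** says reliable contraception is needed even with a history of infertility, "unless due to hysterectomy or because the patient has been postmenopausal naturally for at least 24 consecutive months". The next sentence reads "Two reliable forms of contraception must be used simultaneously, by females", and the only exception attached to it is continuous abstinence.
- **Section 8.2.8 (Black Box Warning)** gives embryo-fetal toxicity as the reason and instructs: "Prevent pregnancy during treatment by the use of two reliable methods of contraception". It gives no menopause limit.

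Sections 3.1.6 and 8.2.9 cover the same drug over the same period: 28 days (4 weeks) before lenalidomide, during therapy and dose interruptions, and 28 days (4 weeks) afterwards.

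**The concern.** One protocol should give one answer to whether a given woman needs the lenalidomide-specific precautions. Here the answer depends on which section the site consults. A coordinator working from the eligibility criteria would place a woman 18 months past natural menopause outside the FCBP rule. A nurse working from the drug-information section would counsel the same woman to use reliable contraception, in two forms.

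The outcome at stake is fetal exposure to a drug with an embryo-fetal boxed warning. Section 11.6 also requires the study to be run exactly as the protocol describes. A site cannot do that when two current sections set different limits for the same woman.

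**Working it through.** The plan has no figure to reproduce. The check sets the two sections side by side and then measures the gap.

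**1. Side by side**

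| | Section 3.1.6 | Section 8.2.9 |
|---|---|---|
| Natural menopause limit | 12 consecutive months | 24 consecutive months |
| What the limit controls | FCBP status, and so the two-method rule | Whether reliable contraception is indicated |
| Two methods | Required of FCBP | Required of females, in the next sentence |
| Exception for abstinence | Yes | Yes |
| Surgical exemption | Hysterectomy or bilateral oophorectomy | Hysterectomy only; oophorectomy not mentioned |

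Both are current protocol text. The figure 12 appears twice in 3.1.6, in the criterion and in its parenthesis, so a single mistyped digit is unlikely.

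**2. Who falls between the limits**

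Take a woman with no relevant surgery who is *m* completed months past natural menopause.

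- *m* below 12: both sections apply their precautions.
- *m* from 12 to 23: 3.1.6 no longer counts her as FCBP, but 8.2.9 still indicates reliable contraception.
- *m* of 24 or more: exempt under both, if the two-form sentence in 8.2.9 is read with the exemption sentence before it.

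**3. Width of the gap**

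24 − 12 = 12 months. Section 4.4 caps treatment at the same length: "Treatment may continue for up to one (1) year or until any of the following occur".

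For a woman who starts at *m* = 12 to 23 and is treated for the full year, treatment months in the gap = 24 − *m*:

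- *m* = 12: 24 − 12 = 12 months
- *m* = 18: 24 − 18 = 6 months
- *m* = 23: 24 − 23 = 1 month

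This counts treatment months only and leaves out the 28 days before and after. It also leaves out a woman who starts below 12 months. One who starts at *m* = 6 would reach 12 months after 12 − 6 = 6 months on treatment. The documents do not say whether FCBP status is then reassessed.

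**4. Scale**

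The documents give no breakdown by sex or menopausal status, so the number of women cannot be estimated. One woman would be 1/35 = 2.9% of maximum enrolment, or 1/20 = 5.0% of the evaluable target. These figures only show what one patient represents; they are not an estimate of impact.

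**The case against.** **The two-method conflict is partly interpretive.** In 8.2.9 the 24-month clause qualifies the sentence on reliable contraception. The two-form sentence is separate and excepts only abstinence. A reader might infer that 8.2.9 expressly sets a 24-month exemption from two methods; it does not. This stands. Even so, the sentences are adjacent and the boxed warning asks for two methods. On the narrowest reading the sections still disagree about when natural menopause ends the lenalidomide-specific requirement.

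**Everyone must use effective contraception anyway.** This also stands. A reader might infer that 3.1.6 frees a woman at 12 to 23 months from contraception altogether. Its opening requirement on all patients rules that out. That requirement does not ask for two methods, so the difference between the sections remains.

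**REMS governs in practice.** Registration and compliance are mandatory (3.1.9, 8.2.7), certified pharmacies may dispense only to authorised patients (8.2.9), and 3.1.6 sends readers to the REMS materials. This limits the risk considerably. But the documents do not state the REMS menopause limit, so it cannot settle which section is right.

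**Eligibility is checked centrally.** Under 11.4 the Quality Assurance Monitor confirms the eligibility criteria before registration. That should make sites agree with one another, but on the 12-month text, and it leaves 8.2.9 unreconciled.

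**Patients are mostly too old for this to matter.** Largely fair. Section 3.1.3 does also admit patients from 18 to under 60 who have a CIRS score of at least 6 or are judged ineligible for cytotoxic chemotherapy.

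**Conclusion.** The inconsistency is real and minor. The two sections set natural-menopause limits of 12 and 24 consecutive months for the same drug over the same period, and no text says which prevails. A woman 12 to 23 months past natural menopause is outside the two-method rule in 3.1.6. She is inside the contraception rule in 8.2.9 and, on a fair reading, inside its two-form rule. Few women, possibly none, would be affected. No sample size, response estimate or other statistical result changes.

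Three further inferences are tempting, and the documents do not support them:

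- **Conflicting pregnancy-testing rules.** Section 8.2.9 sets no menopause cut-off for testing.
- **Opposing statements on bilateral oophorectomy.** Section 8.2.9 does not mention it, which is a gap in wording.
- **Proof that 12 months is the error.** The documents show only that the limits differ. Preferring 24 rests on its being the stricter limit already in the protocol.

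**What to change.** Use one FCBP definition throughout.

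1. Confirm the menopause limit against the mandatory REMS definition.
2. Subject to that, change both 12-month mentions in the 3.1.6 note (the criterion and its parenthesis) to 24 consecutive months.
3. In 8.2.9, make both the reliable-contraception sentence and the two-form sentence refer to FCBP as defined in 3.1.6, in place of a separate list of exemptions. This removes the need to join two sentences by inference and brings bilateral oophorectomy into line.

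The edit is a few words in two sections. At most a few more women would come under the two-method rule and the FCBP-based pregnancy testing in 3.1.7. Two other rules use the same definition and would widen slightly: condom use by male patients with FCBP partners (3.1.6) and gloves for FCBP who handle the drug (8.2.7). Appendix E shows that the sponsor has made similar corrections before, removing an overlap at a creatinine clearance of 30 in Amendment 6 and aligning infusion windows in Amendment 10.

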9.0 Exploratory Studies

9.1 Evaluate the use of NM PET/CT vs CT imaging in PTCL

The endpoint will be a review of the utilized imaging modalities during treatment as a tool of response assessment. All patients will have CT imaging for enrollment and response assessment time points as outlined in Table 4. When both imaging modalities are chosen for a patient (at treating investigator's discretion), response assessment will be compared.

9.2 Validate a new prognostic model for newly diagnosed PTCL.

Variables for prognosis assessment are part of the eligibility checklist including age, race (African-American vs other), histology, and stage. Variables will be assigned points to determine a prognostic score. Survival by prognostic score are separated into three categories with score = 0-1, 2, or 3-5. Points assigned are outline below:

Variable	Determinant	Reference	HR	Points Assigned
Age	>/=55	<54	1.51	1
Race	Black	All others	1.43	1
	AITL	rminant Reference //=55 <54 Black All others AlTL AL	1.19	1
	SCPTL		0.71	0
Histology	ALCL		0.88	1
	HSTL		1.76	2
	EATL		2.32	2
	ATLL		1.34	1
	ENKTL		1.50	2
	T-LGL		0.43	0
	T-PLL		N/A	2
Stage	Distant	Local	1.79	1

9.3 Investigate the tumor immunohistochemical profile to identify potential biomarkers associated with prognosis and treatment response.

9.3.1 Technique

A tissue microarray (TMA) of paraffin-embedded lymphoid tissue biopsies of all patients will be created and analyzed. This TMA will quantify expression of multiple markers in order to determine how such markers correlate with clinical outcome. Proposed analysis includes immunohistochemistry for CD4, CD8, CD5, CD7, CD8, CD15, CD20, CD30, EBER, Ki-67, p53, TIA-1, granzyme B, TCR F1, TNF-α, IL-6, and nm23-H1.

9.3.2 Tissue Collection

Paraffin-embedded tumor samples will be collected from prior diagnostic biopsies prior to enrollment. Construction of the TMA will require 1.0 to 1.5 mm punch cores for proper analysis. Samples will be sent to the Northwestern PathCore facility. Samples from outside institutions may be sent in batches. The analysis will be conducted by our collaborators in hematopathology. Collection of tissues samples is mandatory however if sample is inadequate a repeat biopsy will not be required nor will patients be excluded from clinical trial enrollment.

10.0 Statistical Considerations

10.1 Primary Endpoint & Sample Size Calculations

The primary objective of this phase II trial will be to evaluate the efficacy of the combination of romidepsin plus lenalidomide in patients with previously untreated PTCL. The endpoint for this objective will be objective response rate (ORR), defined per Cheson criteria. Response will be assessed by imaging after cycles 3 and 6, and then every 6 months thereafter. Single agent romidepsin or lenalidomide have response rates of approximately 25% in patients with relapsed/refractory PTCL [3, 44, 45]. However, a recently presented study (unpublished) of the combination of romidepsin and lenalidomide demonstrated an objective response rate in relapsed/refractory PTCL of 50%[46]. The front-line setting has not been tested.

Due to recruitment issues, we will limit the study to n=20 evaluable patients. This will allow us to estimate the underlying true response rate with a half width of an approximate 95% confidence interval equal to 1.96x0.5/sqrt(20) = 1.96x0.11 = 0.22.

10.2 Secondary Endpoints

To evaluate the safety of the combination of romidepsin and lenalidomide, the endpoint will be the frequency and severity of toxicity events using the NCI CTCAE v 4.03. All

adverse events will be summarized as to type, severity, frequency, timing and attribution. Descriptive frequencies and proportions will be used for this analysis.

To further evaluate efficacy of the combination of romidepsin and lenalidomide, the endpoint will be progression-free survival (PFS) and overall survival (OS) at 1 and 3 years after start of treatment as well as the duration of response from start of therapy, defined per Cheson criteria. Kaplan-Meier curves will be determined for progression-free survival and overall survival and the one- and three-year point on this curve, along with 90% confidence limits. Duration of response will be summarized by descriptive statistics in responders (mean, median, range).

To evaluate the delay to cytotoxic chemotherapy, the endpoint will be time to first cytotoxic chemotherapy (TTFCC) from start of treatment. This will be summarized by descriptive statistics (mean, median, range).

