2.2 Secondary Objectives & Endpoints

2.2.1 Evaluate the safety of the combination of romidepsin and lenalidomide.

The endpoint will be the frequency and severity of toxicity events using the NCI CTCAE v 4.03.

2.2.2 Further evaluate efficacy of the combination of romidepsin and lenalidomide.

The endpoints will be progression-free survival (PFS) and overall survival (OS) at 1 and 3 years after start of treatment as well as the duration of response from start of therapy, defined per Cheson criteria.

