4.5 Duration of Follow Up

Once patients are off treatment for any reason, they will have a final off-treatment visit approximately 30 days post-last dose of study therapy. Thereafter, they will be followed with at least one clinic visit every 3 months for up to 1 year from start of treatment, then every 6 months up to 3 years from start of treatment (or until death, whichever occurs first). Patients removed from treatment for unacceptable adverse events will be followed until resolution or stabilization of the adverse event.

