6.2.7 Duration of Response

6.2.7.1 Duration of overall response:

The duration of overall response is measured from the time measurement criteria are met for CR or PR (whichever is first recorded) until the first date that recurrent or progressive disease is objectively documented (taking as reference for progressive disease the smallest measurements recorded since the treatment started).

The duration of overall CR is measured from the time measurement criteria are first met for CR until the first date that recurrent disease is objectively documented.

6.2.7.2 **Duration of stable disease:**

Stable disease is measured from the start of the treatment until the criteria for progression are met, taking as reference the smallest measurements recorded since the treatment started.

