6.2.8 Time to first cytotoxic chemotherapy

Time to first cytotoxic chemotherapy (TTFCC) is defined as the time from start of study treatment to time of first dose of anti-neoplastic cytotoxic chemotherapy that is administered to treat lymphoma. This does not include corticosteroids, antivirals, or chemotherapeutic agents used for either non-neoplastic diseases or other malignant processes (not lymphoma).

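### Duration of response and time to first cytotoxic chemotherapy get raw means and medians with no rule for incomplete times, and duration of response has two start dates

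*Combined protocol and SAP*

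**What the plan says.** Section 10.2 (Secondary Endpoints) assigns Kaplan-Meier curves, with 1- and 3-year estimates and 90% limits, to PFS and OS only. For duration of response: "Duration of response will be summarized by descriptive statistics in responders (mean, median, range". For TTFCC: "This will be summarized by descriptive statistics (mean, median, range".

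Section 2.2.2 describes the first of these endpoints "as well as the duration of response from start of therapy", and Section 10.2 repeats that phrase. Section 6.2.7.1 defines it differently, as "measured from the time measurement criteria are met for CR or PR (whichever is first recorded", and runs it "until the first date that recurrent or progressive disease is objectively documented". Section 6.2.8 defines TTFCC as the "time from start of study treatment to time of first dose of anti-neoplastic cytotoxic chemotherapy that is administered to treat lymphoma".

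Follow-up is limited. Section 4.5 schedules visits every 3 months in the first year, "then every 6 months up to 3 years from start of treatment" or until death. Section 4.4 adds: "Patients who withdraw consent from the study as a whole will be noted to have withdrawn from both treatment and any further follow-up".

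**The concern.** There are two separate defects.

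**No method for incomplete times.** Some responders will still be in response at 3 years, some will withdraw, and some will die without documented progression. Some patients will die without cytotoxic chemotherapy or never need it. Section 6.2.8 gives such patients no TTFCC value, and Section 6.2.7.1 has no rule for death in response. A mean, median and range presuppose that every time is complete. One analyst could enter incomplete times as if complete and another could drop them; both would be following Section 10.2, and they would report different numbers from the same data.

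**Two start dates.** Time from start of therapy and time from first documented CR or PR are different quantities. No section reconciles them, and the amendment history does not either.

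TTFCC is the only endpoint for the objective in Section 2.2.3, the delay to cytotoxic chemotherapy. Section 1.4 cites a median duration of response of 17 months for romidepsin alone, a figure that readers may well set beside this trial's result.

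**Working it through.** The plan states no expected value for either endpoint, so there is no figure to reproduce. The sizes below are illustrations under stated assumptions.

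**1. Start-date gap.** Inputs: 28-day cycles (Section 4.0); scans after cycles 3 and 6, each ±7 days (Section 5.0, footnote 12); 30.4375 days per month.

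- Response first recorded after cycle 3: 3 × 28 = 84 days (77 to 91) = 2.8 months.
- Response first recorded after cycle 6: 6 × 28 = 168 days (161 to 175) = 5.5 months.
- Against the cited 17 months: 2.8/17 = 16% and 5.5/17 = 32%.

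**2. Duration of response, complete follow-up.** Assume exponential times with median M, λ = ln 2/M, no deaths, and response at cycle 3. Follow-up after response is then C = 36 − 2.8 = 33.2 months.

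- Share incomplete = exp(−λC).
- Raw mean with incomplete times entered as observed = (1 − exp(−λC))/λ.
- Median of completed times only = −ln(1 − 0.5(1 − exp(−λC)))/λ.

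For M = 17: λ = 0.0408, exp(−λC) = 0.258, raw mean = 0.742/0.0408 = 18.2.

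| True median | True mean | Incomplete | Raw mean | Completed-only median |
|---|---|---|---|---|
| 6 | 8.7 | 2% | 8.5 | 5.8 |
| 12 | 17.3 | 15% | 14.8 | 9.6 |
| 17 | 24.5 | 26% | 18.2 | 11.4 |
| 24 | 34.6 | 38% | 21.4 | 12.8 |
| 36 | 51.9 | 53% | 24.6 | 14.0 |

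In 20,000 simulated trials with 12 responders and M = 17, the completed-only median averages 11.8 and the median of all times 17.9. The all-times median is therefore nearly unbiased when follow-up is complete and no one dies.

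**3. Duration of response, staggered follow-up.** Assume instead that follow-up after response is uniform over 9 to 33 months, as in an analysis run before everyone reaches 3 years. The expected share incomplete is (exp(−9λ) − exp(−33λ))/(24λ) = (0.693 − 0.260)/0.979 = 0.44, so the raw mean is 24.5 × 0.56 = 13.7. Simulation gives 8.4 for the completed-only median and 13.0 for the all-times median, against a true 17.

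**4. TTFCC.** Assume 20 patients, an exponential median of 18 months to chemotherapy, independent exponential death with median 42 months (the middle of the 3–4 years in Section 1.1), and follow-up to 36 months. Then l = ln 2/18 = 0.0385 and m = ln 2/42 = 0.0165.

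- Neither event by 36 months: exp(−36 × 0.0550) = 14%.
- Death first: 0.30 × (1 − 0.138) = 26%. So 40% have no TTFCC.
- Cumulative incidence of chemotherapy = l/(l+m) × (1 − exp(−(l+m)t)): 0.338 at 12 months and 0.603 at 36 months. It reaches 50% at 22.8 months.
- One minus Kaplan-Meier, censoring deaths, targets 1 − exp(−lt): 0.370 and 0.750.
- In simulation, the completed-only median averages 10.7 and the all-times median 13.1 (18.6 if no one dies).

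With OS medians of 36 to 48 months, the share without an event runs from 42% to 38% and the 36-month incidence from 58% to 62%. With TTFCC medians of 12 to 24 months and OS at 42, the share without an event is 28% to 49% and the all-times median 9.7 to 15.9.

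**The case against.** The strongest reply is that the illustrations may overstate the harm. The 17 months come from romidepsin alone in relapsed or refractory disease, and Section 10.1 says the front-line setting is untested. Section 1.3.3 also cites a median of 6.2 months, for lenalidomide in other lymphomas. At 6 months the raw mean is 8.5 against a true 8.7, which is negligible. This stands: the size depends on how long responses last. The direction does not.

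The OS inputs also sit awkwardly with Section 1.1, which gives 5-year survival below 30%. Exponential medians of 36, 42 and 48 months imply 31%, 37% and 42%. This too is fair, but a shorter OS means more patients die without chemotherapy, so the missing rule matters more.

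The bias in the TTFCC median depends on what is being estimated. The 13.1 months is low against both 18 (no deaths) and 22.8 (cumulative incidence), yet close to the 12.6 months (ln 2/0.0550) for chemotherapy or death combined. That is correct, and it shows the gap: the plan does not say which quantity it wants.

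Other points have partial force. No comparison with the 17 months is planned. Earlier scans are allowed and would narrow the start-date gap. No section says these endpoints will be analysed under staggered follow-up. Finally, the median could be read as a Kaplan-Meier median, but Section 10.2 names that method only for PFS and OS, and the reading does not rescue the mean or range.

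**Conclusion.** Both defects hold as written. The start-date conflict is a direct contradiction between Sections 2.2.2 and 10.2 on one side and Section 6.2.7.1 on the other, worth 2.8 to 5.5 months at the first two scheduled scans. The planned mean is biased downwards wherever times are incomplete: an incomplete time is no longer than the true one, and dropping such times preferentially loses the long ones. For duration of response with complete follow-up, the shortfall runs from 0.2 months at an assumed median of 6 to 6.3 months (24.5 − 18.2) at 17 and 13.2 months (34.6 − 21.4) at 24. The all-times median is acceptable only with complete follow-up and no deaths. These sizes rest on exponential times and assumed medians and are not forecasts for this trial. The text conflict and the missing rules do not depend on them. The plan should be corrected, but the consequences are confined to two secondary endpoints.

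**What to change.** - **Section 10.2, duration of response:** estimate by Kaplan-Meier, with the median and confidence limits, from first documented CR or PR as in Section 6.2.7.1. Censor patients still in response at their last response assessment.
- **Section 6.2.7.1:** state how death in response is counted.
- **Sections 2.2.2 and 10.2:** replace the start-of-therapy wording so that the start date matches Section 6.2.7.1.
- **Section 10.2, TTFCC:** report the cumulative incidence of first cytotoxic chemotherapy at 1 and 3 years with confidence limits (Aalen-Johansen), with death without chemotherapy as a competing event and patients alive without chemotherapy censored at last contact. If the team prefers chemotherapy-free survival, which counts death as an event, it should name and define that endpoint instead.
- **Both endpoints:** delete the raw means.

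The cost is a text amendment and one standard estimator beyond the Kaplan-Meier analysis already planned. No new data are needed: the stated endpoints already require the dates of response, progression, first chemotherapy and death.
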